4.2 METHOD OF TREATMENT ASSIGNMENT AND BLINDING

Both *PSEN1 E280A* mutation carriers and non-carriers are being enrolled. The majority of individuals in the *PSEN1 E280A* kindred from Colombia do not wish to know their *PSEN1* genotype. In most cases, the participant will not know whether he or she is a mutation carrier or a non-carrier. Participants who have their mutation carrier status disclosed by a physician in conjunction with genetic counseling outside of the auspices of this study and are mutation carriers will be eligible for the study. Genetic disclosure performed independent of this study is not required for a mutation carrier to be eligible to participate. Non-carriers who receive information about their genetic status prior to the study will not be included. In view of methods being used to balance groups at enrollment, some otherwise potentially eligible participants may not be included in the study. In cases of genetic disclosure performed independent of this study, some otherwise potentially eligible non-carriers may also not be included in the study.

Participants, blinded study personnel, and the Sponsor will not know if a participant has been assigned to the active treatment or one of the two placebo treatment groups in Study Period A. In Study Period B, participants and blinded study personnel will continue to be blinded to treatment assignment (following database lock for Study Period A, selected members of the Sponsor team may become unblinded for the purpose of analysis and interpretation of the Period A data).

In Study Period A, a dynamic randomization design will be used with treatment allocation assigned by the IxRS vendor. Mutation carriers will be randomized to crenezumab and placebo arms in a 1:1 ratio. A smaller group of mutation non-carriers will be assigned to placebo to conduct the study, such that ADAD family members are not required to receive information about their genetic risk and to help distinguish those changes related to the predisposition to AD from those associated with normal aging in the two placebo groups (in Study Period B, all carrier participants will be assigned crenezumab by the IxRS vendor and non-carrier participants will be assigned placebo).

While PK samples should be collected from participants assigned to the placebo arms to maintain the blinding of treatment assignment, PK assay results for these participants are generally not needed for the safe conduct or proper interpretation of this trial. A defined set of personnel responsible for performing PK assays and not otherwise involved in the conduct of the trial will be unblinded to participants' treatment assignments to identify appropriate PK samples to be analyzed. Samples from participants assigned to the placebo arms will not be analyzed except by request (i.e., to evaluate a possible error in dosing). In addition, PK and plasma PD assay results will not be released to blinded personnel until the study is unblinded.

If unblinding is necessary for participant management (e.g., in the case of an serious adverse event for which participant management might be affected by knowledge of treatment assignment), the investigator will be able to break the treatment code by contacting the IxRS. Treatment codes should not be broken except in emergency situations. If the investigator wishes to know the identity of the study drug for any other reason, he or she should contact the Medical Monitor directly. The investigator should document and provide an explanation for any premature unblinding (e.g., accidental unblinding, unblinding due to an serious adverse event).

For regulatory reporting purposes, and if required by local health authorities, the Sponsor will break the treatment code for all serious, unexpected, and suspected adverse reactions that are considered by the investigator or Sponsor to be related to study drug.

4.3 STUDY TREATMENT

4.3.1 Crenezumab and Placebo

4.3.1.1 Formulation

Crenezumab is produced using Chinese hamster ovary cells—purified and formulated. It is subjected to a series of quality-control tests to confirm its identity, purity, potency, quality, and sterility. The drug product is a sterile, preservative-free liquid intended for SC or IV administration and is formulated as 180 mg/mL crenezumab in 200 mM arginine succinate, 0.05% (w/v) polysorbate 20, pH 5.5. Placebo will consist of the same formulation but without the active drug. Placebo and active drug are supplied in 6-mL glass vials, with 4 mL of liquid per vial.

For further details, see the Crenezumab Investigator's Brochure and the Study GN28352 pharmacy manual.

4.3.1.2 Dosage, Administration, and Storage

Crenezumab will be administered to participants under close medical supervision in a setting with access to appropriate emergency equipment and staff who are trained to monitor and respond to medical emergencies.

Subcutaneous dosing: Crenezumab has been formulated for SC injection, and no dilution of the drug product or placebo is necessary prior to administration.

Administration: Study drug will be administered SC into the back of the arm, the thigh, or the abdomen via polypropylene syringe. The total volume of drug will be 2×2.0 mL (2×360 mg), administered in 2 injections. Vital signs will be measured prior to the injection. Study participants will be observed for a minimum of 30 minutes following the first 4 administrations of study drug (180 mg/mL formulation) and for a minimum of 15 minutes subsequently.

Intravenous dosing: IV infusions will be administered by appropriately trained staff in the clinic.

The IV drug or placebo will be prepared and infused from the IV bag by infusion pump. The bag size, drug preparation, and infusion rates are all described in the pharmacy manual guidance. For the IV dose calculation, the participant's weight should be used. If the current weight changes by $\geq 10\%$ from the previous reference weight, the current weight should become the new reference weight for subsequent dosing. If the participant's weight changes again by $\geq 10\%$ from the reference weight, the IV dose should again be recalculated. See the pharmacy manual for further information.

Administration: Vital signs will be measured just prior to study drug administration, at the end of the IV infusion, and ≥ 60 minutes after the end of the infusion.

Study participants will be observed for a minimum of 60 minutes following IV administration of study drug.

Participants who experience a moderate IRR (e.g., fever or chills) should have the infusion stopped immediately and should receive aggressive symptomatic treatment. The infusion should not be restarted before all symptoms have disappeared, and then it should be restarted at half the initial rate.

Participants who experience serious or severe hypersensitivity reactions (e.g., hypotension, mucosal involvement) should not receive additional study drug. In addition, in any case of anaphylaxis, anaphylactoid reaction, serious or severe hypersensitivity reaction, ADA and concurrent PK samples should be collected as close

as possible to the event, and then at 4 and 16 weeks postdose (see the study flowcharts for further details).

Collection of all relevant clinical data, including vital signs, any change to infusion speeds, etc., should be recorded on the eCRF.

Storage: Vials of study drug should be refrigerated at 2°C–8°C and protected from direct sunlight. Vials should not be frozen or stored at room temperature.

Additional storage details are provided in the pharmacy manual. The pharmacy manual addresses procedures for temperature excursions.

4.3.1.3 Dosage Modification

Participants with a serious, life-threatening adverse event or who meet the criteria for dose discontinuation in Section 3.5.4 must not receive additional doses of study drug (crenezumab or placebo) but will be invited to, and should, remain in the study and complete study assessments per the protocol (see the study flowcharts in [Appendix 1](#), [Appendix 2](#), [Appendix 3](#), and [Appendix 4](#)) if this is deemed to be safe and clinically appropriate by the investigator.

Participants who experience serious or severe hypersensitivity reactions (e.g., hypotension, mucosal involvement) should not receive additional study drug. In addition, in any case of anaphylaxis, anaphylactoid reaction, serious or severe hypersensitivity reaction, ADA and concurrent PK samples should be collected as close as possible to the event, and then at 4 and 16 weeks postdose (see the study flowcharts for further details).

Study drug will be held for participants experiencing other clinically significant neurologic deterioration attributed to the study drug, as judged by the investigator, or other adverse events (including ARIA-E is associated with neurologic symptoms or if BGTS >4, without symptoms). Status will be assessed by MRI follow-up every 4 weeks until symptoms and ARIA-E resolve. Reintroduce study drug and perform an MRI scan after 4 weeks of dosing. If no new ARIA-E is detected, resume MRI monitoring as per study flowcharts.

Any new onset of ARIA-E: Treat the same as the first event, on the basis of symptoms and BGTS. However, in the case where a participant is diagnosed with three recurrent, symptomatic ARIA-E events or exacerbations of previous events, permanently discontinue the study drug. Implement monthly MRI monitoring until resolution of both symptoms and ARIA-E.

ARIA-H

Dose reduction: Participants who develop >8 ARIA-H cumulatively will receive a lower dose of the study drug. Cumulative is the sum of ARIA-H at baseline and newly detected ARIA-H during the study.

Study drug discontinuation: Participants who develop >10 ARIA-H deposition cumulatively will be permanently discontinued from the study drug. Cumulative is the sum of ARIA-H at baseline and newly detected ARIA-H during the study.

The participant will be invited to remain in the study and complete study assessments per the protocol. All such cases should be discussed with the Medical Monitor.

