1.2.2 Clinical Experience

As of May 2021, crenezumab had been investigated in a total of 13 completed studies and 1 ongoing study in Phase I, Phase II, and Phase III clinical trials.

Approximately 1789 patients and healthy volunteers have been exposed to crenezumab in these studies.

Thirteen studies have been completed, including Phase I studies (ABE4427g, AB4662g, GP29172, GP29523, GN29632, GP40201, and JP29973), Phase II studies (ABE4869g, ABE4955g and GN28525) and Phase III studies (BN29552, BN29553 and BN40031). Study GN28352 is ongoing.

Study ABE4427g studied the safety, tolerability, and pharmacokinetics of single- and multiple-ascending doses of crenezumab IV in patients with mild to moderate AD who were 50–86 years of age. Study ABE4662g studied the pharmacokinetics of IV and SC dosing and the relative bioavailability of crenezumab (SC dosing) in healthy volunteers who were 18–50 years of age. Study GP29172 evaluated the pharmacokinetics of SC dosing and the bioequivalence of 2 formulations of crenezumab (SC dosing) in healthy volunteers who were 18–65 years of age. Study GP29523 assessed the tolerability and pharmacokinetics of a single, dose-escalated, SC administration of crenezumab in healthy volunteers. Study GN29632 evaluated the safety and tolerability of multiple doses of crenezumab in patients with mild to moderate AD with doses of 30, 45, 60, and 120 mg/kg IV Q4W. The 13-week double-blinded, dose-escalation part of the study was followed by an OLE part.

Study GP40201 was a Phase I, multicenter, partially blinded, placebo-controlled study designed to assess the safety, tolerability, and pharmacokinetics of SC administered crenezumab while varying dose, injection volume, flow rate, and the use of recombinant human hyaluronidase in healthy volunteers.

Study JP29973 was a Phase I, double-blind, placebo-controlled, randomized, dose-escalation study investigating the safety of repeated doses of crenezumab for 13 weeks in 8 Japanese patients with mild to moderate AD.

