1.2.2.1 Safety Experience in Patients with Sporadic AD

Overall, in all ongoing and completed studies in patients with sporadic AD, crenezumab was well-tolerated. Adverse events occurred across different MedDRA System Organ Class (SOC) groups and were predominantly of mild to moderate severity. No dose relationship was observed with respect to the nature, severity, and frequency of adverse events across crenezumab studies. In patients with sporadic AD, the most commonly reported adverse events were as expected in elderly patients with prodromal, mild, or moderate AD.

A high-level summary of safety data is provided below. Up-to-date safety information from crenezumab studies, including the Phase II and Phase III studies, is provided in the most recent Crenezumab Investigator's Brochure.

Amyloid-Related Imaging Abnormalities

Overall, in the completed studies with a control arm, the frequency of ARIA-H was balanced between treatment arms and was as expected in an AD population.

The majority of ARIA-H findings were asymptomatic.

Overall, the incidence of ARIA-E in crenezumab studies was low. Across all crenezumab studies, as of 12 December 2019, 5 patients were diagnosed with new ARIA-E. All events were mild with a low Barkhof Grand Total Score (BGTS). In the two Phase III Studies BN29552 and BN29553, 2 ARIA-E were reported in the active arms and 1 ARIA-E in the placebo arm. One event of ARIA-E was symptomatic (worsening of headache, in a patient in the active arm of Study BN29552). One patient who was diagnosed with ARIA-E during the double-blind part of the Phase II program (Study ABE4869g) developed recurrent ARIA-E during the OLE phase (Study GN28525). In the 4 other patients, ARIA-E resolved within 5 weeks without recurrence.

Please refer to the current Crenezumab Investigator's Brochure for further details on the incidence of ARIA in crenezumab studies.

Pneumonia

An imbalance in serious adverse events of total lower respiratory tract infections (TLRTI) (including the MedDRA Preferred Terms (PT) of pneumonia, lower respiratory tract infection [LRTI], and bronchitis) driven by pneumonia was observed in the randomized, placebo-controlled portion (RPCP) of the Phase II program. However, this imbalance was not replicated in the pooled data of the two large Phase III Studies (BN29552 and BN29553) where the pneumonia cases were balanced between the active treatment and placebo arms (13 and 15 cases, respectively).

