3.5.2.2 Management of Amyloid-Related Imaging Abnormalities

Amyloid-Related Imaging Abnormalities—Edema/Effusion (ARIA-E)

The following rules for the management of MRI-related findings apply for ARIA-E:

- Asymptomatic ARIA-E with Size < 4 BGTS (Barkhof et al. 2013)
 - Continue study drug at the same dose (i.e., 60 mg/kg crenezumab)
 - Repeat MRI 4 weeks later
 - If ARIA-E is stable or decreased, continue study drug and monthly MRI monitoring until event resolves. Once ARIA-E completely resolves, conduct MRI monitoring as per study flowchart.
 - If ARIA-E increases (BGTS ≥ 4) or symptoms develop, see the rules below.
- Symptomatic ARIA-E (of any size) or asymptomatic ARIA-E with size ≥ 4 BGTS:
 - Temporarily interrupt study drug and implement monthly MRI monitoring
 - Once symptoms and ARIA-E resolve, reintroduce study drug and perform an MRI after 4 weeks of dosing. If no new MRI abnormality is detected, resume MRI monitoring as per the study flowchart.
- For any new onset of ARIA-E:
 - Treat the same as the first event, on the basis of symptoms and BGTS

- If a participant is diagnosed with 3 recurrent, symptomatic ARIA-E events or exacerbations of previous events, permanently discontinue the study drug
- Implement monthly MRI monitoring until resolution of both symptoms and ARIA-E
- As per the protocol, maintain the participant in the study until study end and perform assessments as per the study flowcharts

Amyloid-Related Imaging Abnormalities–Hemosiderin Deposition (ARIA-H)

The following dose adjustments and discontinuation rules for MRI-related findings will apply to ARIA-H:

- Dose reduction: Participants who develop >8 ARIA-H cumulatively will receive a lower dose of the study drug. Cumulative is the sum of ARIA-H at baseline and newly detected ARIA-H during the study.
- Study drug discontinuation: Participants who develop >10 ARIA-H cumulatively will be permanently discontinued from the study drug. Cumulative is the sum of ARIA-H at baseline and newly detected ARIA-H during the study.

The Sponsor believes that the above rules, coupled with frequent MRI monitoring and collection of CNS symptoms, will ensure safety while trying to maximize benefit for the participants.

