Appendix 4 (IV Dosing) Study Flowchart (Week 108–End of Study Period A) (cont.)

- ¶ Includes amphetamines, barbiturates, benzodiazepines, cannabinoids, cocaine, and opioids.
- ¶ Urine pregnancy test must be administered and have a negative result prior to any study drug administration. If the participant has discontinued study drug but is continuing with study assessments, the urine pregnancy test may be deferred except for visits during which FDG-PET or florbetapir PET are administered. Serum and urine pregnancy testing will apply to all women unless documented (by medical records or physician's note) to be surgically sterile or postmenopausal as defined in Section 3.5.5.
- ¶ Vital signs will include measurements of temperature, heart rate, respiratory rate, and systolic and diastolic blood pressure while the participant has been supine for ≥3 minutes. On study drug administration days, record vital signs just prior to IV infusion, at the end of IV infusion, and ≥ 60 minutes after the end of the IV infusion.
- ¶ Participants will be observed for a minimum of 60 minutes following administration of study drug by IV infusion.
- ¶ Although visit windowing for dosing days allows for ± 5 days around any expected visit day, the interval between study drug administrations from 1 monthly visit to the following monthly visit must be between 21 and 35 days.
- ¶ During the treatment period: Participants who develop ≥ 8 amyloid-related imaging abnormalities hemosiderin deposition cumulatively will receive a lower dose of the study drug. Participants who develop ≥ 10 amyloid-related imaging abnormalities-hemosiderin deposition cumulatively will be permanently discontinued from the study drug. Cumulative is the sum of amyloid-related imaging abnormalities hemosiderin deposition at baseline and newly detected amyloid-related imaging abnormalities-hemosiderin deposition during the study.
- ¶ Following transition from SC to IV (higher dose) administration, participants should receive an MRI scan after 3 and 6 months of initiation of IV treatment. Thereafter, MRI should be scheduled every 24–28 weeks until the end of the study or ET.
- ¶ Urine pregnancy test must be administered and have a negative result prior to a PET scan. It is recommended, but not required, to use effective contraception during sexual intercourse occurring within 24 hours following a male or female participant receiving a florbetapir PET or FDG-PET scan

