Next, we show through simulations *to support the proof*. For simplicity, we assume the BP analysis is performed on 2 endpoints X and Y , where the experimental drug has no treatment effect on X but *could have* a treatment effect on Y .

Mimicking study GN28352, we assume the following:

- 84 participants randomized to the placebo arm and 84 participants randomized to the experimental arm, with no dropout
- Endpoints X and Y both follow a normal distribution within each arm
- Within endpoints X and Y , without loss of generality, the standard deviation in both arms is 1
- Endpoint X has no treatment effect and the placebo arm mean is 1/0.65 (protocol CV assumption on API ADAD Composite Cognitive Test total score=0.65)

In the simulation study, we vary the following, which yields 135 scenarios:

- Treatment effect in endpoint Y in RR scale: 0%, 50%, and 100%
- Placebo mean in endpoint Y : 0, 1, 1.5, 2, 10
- *Endpoints X and Y follow a bivariate normal distribution with*
 - Correlation between endpoint X and Y within the placebo group: $\rho_{pbo}=0.1, 0.5, 0.9$
 - Correlation between endpoint X and Y within the treatment group: $\rho_{exp}=0.1, 0.5, 0.9$

The family-wise type I error in this case equals the probability of rejecting the null H_0 in endpoint X . *When there is a treatment effect in endpoint Y , the only scenario where a type I error can happen is when endpoint X is chosen by the BP analysis.* The number of iterations in the simulation study was 100,000. We summarize the simulation results on type I error (along with the probability of choosing endpoint Y *in scenarios where endpoint Y has a treatment effect*) in [Tables 1–3](#).

Table 1 Family-Wise Strong Type I Error, Assuming 0% Treatment Effect in Endpoint Y (Type I Error in the Weak Sense)

		Placebo Mean in Endpoint Y				
		0	1	1.5	2	10
$\rho_{pbo} = 0.1$	$\rho_{exp} = 0.1$	0.05090	0.04968	0.0583	0.04965	0.04862
	$\rho_{exp} = 0.5$	0.04928	0.04963	0.04995	0.05029	0.04983
	$\rho_{exp} = 0.9$	0.05042	0.04981	0.05012	0.04894	0.05068
$\rho_{pbo} = 0.5$	$\rho_{exp} = 0.1$	0.04949	0.04898	0.04953	0.04982	0.05075

		Placebo Mean in Endpoint Y				
	$\rho_{exp} = 0.5$	0.05052	0.05048	0.05014	0.04953	0.04962
	$\rho_{exp} = 0.9$	0.04913	0.05105	0.05016	0.04927	0.04969
$\rho_{pbo} = 0.9$	$\rho_{exp} = 0.1$	0.05074	0.05068	0.05055	0.04959	0.05099
	$\rho_{exp} = 0.5$	0.05010	0.05002	0.05012	0.04951	0.05088
	$\rho_{exp} = 0.9$	0.04969	0.05063	0.04900	0.05004	0.04970

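### Section 4.3.1.3 holds study drug for asymptomatic ARIA-E only above BGTS 4, while the synopsis and Section 3.5.2.2 interrupt it at 4 or more

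*Protocol*

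**What the plan says.** Protocol Section 3.5.2.2 gives a graded rule for ARIA-E, and the synopsis repeats it. Below BGTS 4 without symptoms, dosing continues and the MRI is repeated after 4 weeks. The escalation step reads "If ARIA-E increases (BGTS ≥ 4) or symptoms develop, see the rules below". The category that requires temporary interruption and monthly MRI is "Symptomatic ARIA-E (of any size) or asymptomatic ARIA-E with size ≥ 4 BGTS". These three statements all place the limit at 4, with 4 itself on the interrupt side.

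Section 4.3.1.3 restates the hold. Drug is held for ARIA-E with neurologic symptoms, "or if BGTS >4, without symptoms", with MRI every 4 weeks until resolution. The section gives no rule for ARIA-E below its trigger and does not refer to Section 3.5.2.2. The only numbered section it cites is in the clause on participants "who meet the criteria for dose discontinuation in Section 3.5.4", and Section 3.5.4 covers injection and infusion reactions. Nothing in the protocol says which section prevails.

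**The concern.** Section 4.3.1.3 carries the title under which a site would look up a dose hold. At a score of exactly 4 without symptoms its stated trigger is not met, and its 4-weekly MRI follow-up is tied to the hold. A site relying on it could therefore miss both the interruption and the early repeat scan that Section 3.5.2.2 requires.

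The participant would then fall back on the routine MRI schedule in Section 3.5.2.1. After the first year of Period A that is about every 6 months, or every 24–28 weeks on established IV dosing. In Period B it is Week 105 and otherwise as symptoms direct. Section 4.3.1.3 also handles recurrences like the first event, so its threshold carries over to them.

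ARIA-E is a protocol-defined event of special interest (Section 5.1.3). The rule still matters under Version 11, because all carriers who enter Period B receive crenezumab, including those previously on placebo. What is at stake is participant management. ARIA-E is diagnosed by the central MRI reader, so ascertainment does not change.

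**Working it through.** **Comparison of the rules.** The plan gives no figure to reproduce, so the texts are set side by side for asymptomatic ARIA-E.

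| BGTS | Synopsis and Section 3.5.2.2 | Section 4.3.1.3 |
|---|---|---|
| Below 4 | Continue; repeat MRI at 4 weeks | Trigger not met; no rule given |
| Exactly 4 | Interrupt; monthly MRI | Trigger not met; no rule given |
| Above 4 | Interrupt; monthly MRI | Hold; MRI every 4 weeks |

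The texts part only in the middle row.

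The flowcharts do not settle it. The footnotes to Appendices 1–4 repeat the ARIA-H count rule but give no ARIA-E score, and those to Appendices 5 and 6 give neither. The ARIA-E threshold therefore appears in three places (synopsis, 3.5.2.2 and 4.3.1.3), and one of them differs.

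**How often it could arise.** Inputs:

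- ARIA-E cases: Section 1.2.2.1 reports that "5 patients were diagnosed with new ARIA-E" across all crenezumab studies to 12 December 2019, all with low BGTS. One of the Phase III cases was on placebo, so at most 5 − 1 = 4 were on crenezumab.
- Exposed: "Approximately 1789 patients and healthy volunteers have been exposed to crenezumab in these studies" (Section 1.2.2, as of May 2021).
- Arm size: the SAP Appendix 2 simulation, which mimics this study, uses "84 participants randomized to the placebo arm and 84 participants randomized to the experimental arm, with no dropout".

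Crude rate = cases / exposed:

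- crenezumab cases only: 4 / 1789 = 0.00224 (0.22%)
- all five cases: 5 / 1789 = 0.00279 (0.28%)

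Expected ARIA-E cases = number treated × rate:

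| Setting | Using 4 cases | Using 5 cases |
|---|---|---|
| Crenezumab arm of 84, crude rate | 84 × 0.00224 = 0.19 | 84 × 0.00279 = 0.23 |
| Same arm, rate assumed 10 times higher for longer follow-up | 1.9 | 2.3 |
| All 84 + 84 = 168 carriers on crenezumab in Period B, crude rate | 0.38 | 0.47 |

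These counts cover ARIA-E of any score. Asymptomatic cases at exactly 4 are a subset of them, and the documents give no distribution from which to size that subset.

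**The case against.** The strongest objection is that the discrepancy rests on one character in machine-read text. If ≥ was read as > in Section 4.3.1.3, the conflict disappears and only a missing cross-reference remains. Section 4.3.1.3 contains no ≥ to show that the symbol was read correctly there. This stands as a reason to check the source file, but it does not show an error in reading: ≥ came through correctly in the adjacent Section 4.3.1.2, and the > signs in the ARIA-H rules of Section 4.3.1.3 match those in Section 3.5.2.2.

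Second, no site is forced into a breach. Section 4.3.1.3 never orders continuation at 4, and its list of events is introduced as non-exhaustive, so holding at 4 complies with every section. A site that finds no answer there would be expected to turn to Section 3.5.2.2. This is correct, and it limits the finding to what a site could do. It does not reconcile the two thresholds.

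Third, Section 5.1.3 requires every ARIA-E event, whether or not serious, to reach the sponsor within 24 hours, and it points to Section 3.5.2. That is a real safeguard and makes prolonged dosing at 4 less likely, but the conflicting instruction remains.

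Fourth, the rate is weak. The 1789 exposed include healthy volunteers, the two cut-off dates differ, the tenfold factor is arbitrary, and 84 per arm is a simulation input. Period B has few scheduled scans, so asymptomatic cases would seldom be found there. All of this stands. The figures serve only to show that few participants could be affected.

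**Conclusion.** The inconsistency holds as the text reads. At BGTS 4 without symptoms, the synopsis and Section 3.5.2.2 require interruption, while the stated trigger in Section 4.3.1.3 is not met.

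Its size is small: roughly 0.2 ARIA-E cases of any score in the crenezumab arm at the crude programme rate, about 2 under the assumed tenfold rate, and fewer at exactly 4. Confidence is medium, because the conclusion assumes that the symbol in the source file is indeed >.

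It should still be corrected, because it is an operative safety threshold and the correction costs very little.

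**What to change.** Check the symbol in Section 4.3.1.3 against the source file. If it is >, change it to ≥ 4, add a reference to Section 3.5.2.2 as the governing ARIA rule, and notify the sites. The cost is one symbol and one cross-reference in the next amendment, with a short clarification letter in the meantime to the primary site and its approximately three satellites. If the source already reads ≥, only the cross-reference remains worth adding.

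In the same check, confirm the ARIA-H symbols in the footnotes to the Appendix 3 IV flowchart, which carry an Appendix 4 running header. They read "Participants who develop ≥ 8 amyloid-related imaging abnormalities hemosiderin deposition cumulatively will receive a lower dose of the study drug" and, for permanent discontinuation, ≥ 10. Sections 3.5.2.2 and 4.3.1.3 use > 8 and > 10. That difference may come from text extraction and is not claimed here as an error.
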